**Table 5 Pre-specified Criteria**

Term	Criteria
ALT (U/L)	$\leq 3 \times \text{ULN}$ $>3 \text{ to } \leq 5 \times \text{ULN}$ $>5 \text{ to } \leq 20 \times \text{ULN}$ $>20 \times \text{ULN}$
AST (U/L)	$\leq 3 \times \text{ULN}$ $>3 \text{ to } \leq 5 \times \text{ULN}$ $>5 \text{ to } \leq 20 \times \text{ULN}$ $>20 \times \text{ULN}$
Total Bilirubin (mg/dL)	$<1.5 \times \text{ULN}$ $\geq 1.5 \text{ to } <3 \times \text{ULN}$ $>3 \text{ to } \leq 10 \times \text{ULN}$ $>10 \times \text{ULN}$
AST (U/L) or ALT (U/L)	$\leq 3 \times \text{ULN}$ $>3 \text{ to } \leq 5 \times \text{ULN}$ $>5 \text{ to } \leq 20 \times \text{ULN}$ $>20 \times \text{ULN}$
AST (U/L) or ALT (U/L) and Total bilirubin (mg/dL)	Meet all of the following criteria: 
 
• AST <math>> 3 \times \text{ULN}</math> or ALT <math>> 3 \times \text{ULN}</math>
 
• Total bilirubin value <math>> 2 \times \text{ULN}</math>
 

ULN = upper limit of normal.

### 10.3 Vital Signs

For each of the vital signs (diastolic blood pressures, systolic blood pressures, respiratory rate and pulse rate), summary statistics of observation and the change from baseline will be presented by treatment group at each scheduled time point. For each of the vital sign parameters, the plot of the baseline value and last observation value is presented for all patients in the safety population. Last observation value is defined as the value at the last time point in all observed time points within acceptable window and the time point of early termination within acceptable window.

### 10.4 Electrocardiography (ECG)

The frequency of each ECG findings will be summarized by treatment group at each scheduled time point. Each ECG findings will be classified into three categories: “normal,” “abnormal-not clinically significant,” and “abnormal-clinically significant.”

### 10.5 Subgroup Analyses for Safety Endpoint

Analyses of adverse events (Section 10.1 1) and 2), except proportion of patients who experienced AEs of 2% or higher) will be presented for the following subgroup 1) and 2).

Subgroup analyses will be performed for the Safety population.

- 1) Body weight
  - < 80 kg
  - ≥ 80 kg
- 2) Age
  - < 18 years
  - ≥ 18 years

## 11. INTERIM ANALYSES

No interim analysis is planned in this study.

## 12. PROGRAMMING SPECIFICATIONS

Unless otherwise specified, the following conventions should be used when constructing the analysis tables, figures and listings are prepared:

- Every summary table and figure should clearly specify the analysis population being summarized. Listings will be prepared for all patients randomized.
- Treatment group of the S-033188 in the listings will be reported as following rules.
  - S-033188 40 mg: Kit number (1) was assigned and the S-033188 was administered
  - S-033188 80 mg: Both kit number (1) and (2) were assigned and the S-033188 was administered

- Number of digits to be displayed for calculated values

For the following endpoints, data will be rounded off to 8 decimal places, and the rounded values will be used for analysis. Table 6 is shown the summary of the number of digit displayed for each endpoint.

**Table 6 Summary of the Number of Digits Displayed for Endpoints**

Endpoint	No. of digits displayed (after the decimal point)		
	Minimum Maximum	Mean Median	SD CI
Time to alleviation of symptoms			
Time to cessation of viral shedding by virus titer/ RT-PCR			
Time to alleviation of the 4 systemic symptoms			
Time to alleviation of the 3 respiratory symptoms			
Time to resolution of fever			
Time to alleviation of individual symptoms			
Time to return to preinfluenza health status			
Area under the curve adjusted by baseline in virus titer	1	1	1
Area under the curve adjusted by baseline in the amount of virus RNA (RT-PCR)			
Drug susceptibility in patients with evaluable virus: the ratio of EC50/IC50 at baseline relative to EC50/IC50 for reference			
Time Required for Personal Assistance Due to Influenza Illness			
Index value			
Percentage of absenteeism due to influenza illness	3	3	3
Percentage of work productivity loss due to influenza illness			
Change from baseline in influenza virus titer	2	2	2
Change from baseline in amount of virus RNA			
Treatment compliance rate	1	2	2

Summary statistics will be displayed to the number of digits as shown in Table 7.

**Table 7 Summary of the Number of Digits Displayed**

	No. of digits displayed
p value	Round off to 4 decimal places. However, p value of <0.0001 will be displayed as “<.0001.”
No. of subjects	Display as a whole number.
Mean, SD, median, adjusted mean, SE, 95% CI	One decimal place beyond the number of decimal places with which the original endpoint is presented.
Minimum, maximum	Same number of digits of the observed data
Percentage (%)	Round off to 1 decimal place.

- Categories used for summarization

Basically, categories described in CRFs will be used for summarization. If data need to be categorized, the data should be categorized according to Table 8 below.

**Table 8 Category of Variable**

Variable	Category
Age	12-19 years, 20-29 years, 30-39 years, 40-49 years, 50-59 years, 60-64 years
Body weight	<80 kg, ≥80 kg
Timing of meal before and after dosing	<2 hours, 2 to 4 hours, > 4 hours
Time of onset of influenza symptoms	0-12 hours, 12-24 hours, 24-36 hours, 36-48 hours
Influenza virus subtype based on RIDT	A, B, A and B, Negative, Unknown
Influenza virus subtype based on RT-PCR	A/H1N1pdm: A/H1N1pdm A/H3: A/H3 B:B Mixed infection: A/H1N1pdm and B, A/H3 and B, A/Unknown and B, A/ND and B, A/H1N1pdm and A/H3 and B, A/H1N1pdm and A/H3 Other: A/Unknown, A/ND, Unknown Negative:
	The above virus subtype classification is derived from the following specification:
	- A/H1N1pdm: H1_2009
	- A/H3: H3
	- A/H1N1pdm and A/H3: H1_2009/H3
	- A/ND: ND
	- A/Unknown: UNKNOWN
Virus subtype classification used for subgroup analysis	A/H1N1pdm, A/H3, B
Serum influenza antibody titer (Day 1, Day 22)	<10, ≥10 to <20, ≥20 to < 40, ≥40 to < 80, ≥80 to <160, ≥160
Serum influenza antibody titer (Ratio of Day 22 relative to Day 1)	<4, ≥4 to <8, ≥8 to <16, ≥16 to <32, ≥32 to <64, ≥64 to <128, ≥128 to <256, ≥256
Composite symptoms score at baseline	≤11, ≥12
Treatment compliance rate	<80, ≥80
Acetaminophen use	0, 1-2, 3-4, ≥5
Time of onset of AE	Week 1 (≥1 day to <8 days), Week 2 (≥8 days to <15 days), Week ≥3 (≥15 days)
Urine protein	-, 1+, 2+, 3+, Unknown
Urine glucose	-, 1+, 2+, 3+, 4+, Unknown
Urobilinogen	-, 1+, 2+, 3+, 4+, Unknown
Urine occult blood	-, 1+, 2+, 3+, 4+, Unknown

### **13. BLINDED REVIEW**

PCR positive rate at baseline will be estimated during the study.

### **14. SUMMARY OF CHANGES FROM PROTOCOL SPECIFIED ANALYSIS**

In Protocol section 9.11.1, the following analysis will be changed.

- The summary for action taken with the study drug will be presented by system organ class and preferred term. Due to single dose of S-033188, this analysis is not performed.

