- S-033188 20-mg tablets

Control Drugs

- Oseltamivir 75-mg capsules
- Placebo tablet matching S-033188 20-mg tablets
- Placebo capsule matching oseltamivir 75-mg capsules

All patients will receive the study drug provided for each group according to the result of allocation.

Patients aged ≥ 20 years

[S-033188 group]

- Day 1: Two or four 20-mg S-033188 tablets (depending on weight) will be administered orally. One oseltamivir placebo capsule will be administered orally BID (morning and evening).
- Days 2 to 5: One oseltamivir placebo capsule will be administered orally BID (morning and evening).

[Oseltamivir group]

- Day 1: Two or four S-033188 placebo tablets (depending on weight) will be administered orally. One 75-mg oseltamivir capsule will be administered orally BID (morning and evening).
- Days 2 to 5: One 75-mg oseltamivir capsule will be administered orally BID (morning and evening).

[Placebo group]

- Day 1: Two or four S-033188 placebo tablets (depending on weight) will be administered orally. One oseltamivir placebo capsule will be administered orally BID (morning and evening).
- Days 2 to 5: One oseltamivir placebo capsule will be administered orally BID (morning and evening).

Patients aged 12 to 19 years

[S-033188 group]

Day 1: Two or four 20-mg S-033188 tablets (depending on weight) will be administered orally.

[Placebo group]

Day 1: Two or four S-033188 placebo tablets (depending on weight) will be administered orally.

Duration of Treatment:

Patients aged 20 to 64 years: 5 days

Patients aged 12 to 19 years: 1 day

Prohibited Concomitant Therapy:

The use of the following drugs and over-the-counter drugs with equivalent efficacy to them will be prohibited from Visit 1 (Day 1) until Visit 7 (Day 22) or early termination.

- a. Systemic antiviral drugs
 - b. Antimicrobial* and antifungal drugs**
 - c. Antipyretics/analgesics except acetaminophen
 - d. Antitussives/expectorants
 - e. Combination cold remedies
 - f. Antihistamines**
 - g. Corticosteroids**
 - h. Immunosuppressants
 - i. Herbal medicines or complementary therapies indicated for influenza virus infection (eg, Maoutou)
 - j. Other investigational drugs
- * Except for the treatment of complications of influenza suspected to be bacterial infection after Day 1.
- ** Dermal preparations will be permitted, but application to the eyes, nose or ears, or by inhalation will be prohibited.

Efficacy Assessments:

Primary endpoint:

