3. INVESTIGATIONAL PLAN

3.1 Overall Study Design and Plan

This study is a randomized, double-blind, multicenter, parallel-group, placebo- and active-controlled study designed to evaluate the efficacy and safety of single dose of S-033188 in otherwise healthy adult and adolescent patients with influenza virus infection.

Prior to the initiation of the study treatment on Day 1, patients will be assessed for eligibility for participation in the study. Patients aged 20 to 64 years who are determined to be eligible will be randomly assigned in a ratio of 2:2:1 to receive a single dose of S-033188 (either 40 mg or 80 mg according to weight), 75 mg BID of oseltamivir for 5 days, or placebo. Patients aged 12 to 19 years who are determined to be eligible will be randomly assigned in a ratio of 2:1 to receive a single dose of either 40 or 80 mg of S-033188 or placebo. Patients who weigh < 80 kg at Screening will receive 40 mg of S-033188, and patients who weigh ≥ 80 kg at Screening will receive 80 mg of S-033188. The study drug will be administered orally at the study center on Day 1 (initial dose). Patients aged 20 to 64 years will receive study drug twice daily for 5 days in total. For patients aged 12 to 19 years, a single dose of study drug will be tested. There is a maximum of 9 visits including 2 optional visits during a period to assess the efficacy and safety: 14 days for efficacy and 22 days for safety. The study schematic is shown in Figure 3-1. The time and events schedule is provided in Appendix 1.

Figure 3-1 Study Schematic

This study will be conducted in compliance with this protocol, International Conference on Harmonisation-Good Clinical Practices (ICH-GCPs), and all applicable requirements.

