5.2 Treatments to be Administered

5.2.1 Patients Aged 20 to 64 Years

Patients who are qualified for entry will be randomly assigned in a ratio of 2:2:1 to receive S-033188, oseltamivir, or placebo according to the assignment procedures specified in Section 5.4. Patients will receive S-033188 or placebo once on Day 1. Oseltamivir or placebo should be dosed 12 hours apart from Day 1 through Day 5. The details of administration are shown in Table 5-1. Study drugs can be taken without regard to food (although food may improve tolerability of oseltamivir).

Patients should be instructed that in the case of missed doses of oseltamivir/placebo they should take the missed dose as soon as they remember, unless it is 2 hours or less before the next dose. They should then continue to take oseltamivir/placebo at the usual times. Patients should not take 2 doses at a time to make up for a missed dose.

Table 5-1 Study Drug Administration (Patients Aged \geq 20 Years)

Treatment Group	Day 1	Day 2	Day 3	Day 4	Day 5*
S-033188					
Oseltamivir placebo S-033188 40 mg (weight < 80 kg)	2 capsules				
S-033188 80 mg (weight \geq 80 kg)	4 tablets				
Oseltamivir					
Oseltamivir 75 mg S-033188 placebo (weight < 80 kg)	2 capsules				
S-033188 placebo (weight \geq 80 kg)	4 tablets				
Placebo					
Oseltamivir placebo S-033188 placebo (weight < 80 kg)	2 capsules				
S-033188 placebo (weight \geq 80 kg)	4 tablets				

* If only 1 dose of oseltamivir or placebo is taken on Day 1 due to the patient being randomized after 17:00, dosing will be completed on Day 6.

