9.11.1 Adverse Events

AEs will be classified by system organ class and preferred term using Medical Dictionary for Regulatory Activities (MedDRA). Of reported AEs on the eCRF, AEs reported after the initial dose of randomized study drug will be used for safety analyses.

The number of patients who experience at least 1 AE, deaths, other SAEs, and AEs leading to withdrawal will be counted for each treatment group. The incidences and their 95% CI will be calculated by using the Clopper-Pearson method. The number of those AEs, which are counted by cases reported, will also be presented. Treatment-related AEs will be summarized in the same manner as AEs described above.

The number and percentage of patients who experience AEs by MedDRA system organ class and preferred term will be presented for each treatment group. The summary for action taken with the study drug, timing of onset, severity, and outcome will be presented by system organ class and preferred term.

All AEs, including those occurring prior to the initiation of the study treatment, will be listed.

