## 2. OVERVIEW

This is a randomized, double-blind, multicenter, parallel-group, placebo- and active controlled study enrolling approximately 1494 patients diagnosed with influenza. Approximately 1350 patients aged 20 to 64 years and 144 patients aged 12 to 19 years will be enrolled. Patients in 20 to 64 years age stratum will be randomly assigned in a ratio of 2:2:1 to receive a single dose of 40 or 80 mg of S-033188 according to their weight category, 75 mg BID of oseltamivir for 5 days, or placebo. With the aim to achieve a broadly comparable exposure, patients who weigh < 80 kg at Screening will receive 40 mg of S-033188, and patients who weigh  $\geq$  80 kg at Screening will receive 80 mg of S-033188. Patients in 12 to 19 years age stratum will be randomly assigned in a ratio of 2:1 to receive a single dose of 40 or 80 mg (depending on weight) S-033188 or placebo.

For the schedule of this study, see Appendix 1.

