### 10.1 Adverse Events

AEs will be classified by system organ class and preferred term using Medical Dictionary for Regulatory Activities (MedDRA) Version 19.1. Of reported AEs on the eCRF, AEs reported after the initial dose of study drug will be used for safety analyses.

- 1) The number and proportion of patients who experienced at least 1 AE will be tabulated by treatment group. Their 95 % CIs will also be calculated with Clopper-Pearson method. In addition, the proportion will be compared with placebo group or oseltamivir group by using Fisher's exact test will be calculated. The number of events will also be tabulated. Death, other serious AEs, AEs

leading to withdrawal of the study drug, and treatment-related AEs will be summarized in the same manner as the overall summary of AEs. The definition of death, serious AEs, AEs leading to withdrawal, other severe AEs, treatment-related AEs are shown below.

Term	Definition
Death	AEs with “Fatal” in terms of outcome.
Other serious AEs (Serious AEs excluding death)	AEs with “Serious” in terms of seriousness excluding death
AEs leading to withdrawal of the study drug	AEs with “Drug withdrawn” in terms of the action taken for study drug.
Treatment-related AEs	AEs with “Related” in terms of the causal relationship with study drug.

- 2) The number and proportion of patients who experienced AEs will be tabulated by system organ class (SOC) and preferred term (PT) for each treatment group. For these summaries, patients with multiple AEs will be counted only once within an SOC and PT. Serious AEs, Treatment-related AEs and serious treatment-related AEs will be summarized in a similar manner. In addition, proportion of patients who experienced AEs of 2% or higher in any the dose treatment groups will be tabulated by SOC and PT.

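### The SAP drops the summary of action taken with study drug because S-033188 is a single dose, a reason that does not fit the adults, who take capsules for five days

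*SAP*

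**What the plan says.** Protocol 9.11.1 sets out the AE tables: "The summary for action taken with the study drug, timing of onset, severity, and outcome will be presented by system organ class and preferred term". SAP 14 lists a single change from the protocol's analyses, which is to remove the action-taken part of that summary. The reason given is "Due to single dose of S-033188, this analysis is not performed".

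The dosing sections describe a longer course for adults. Protocol 3.1 states: "Patients aged 20 to 64 years will receive study drug twice daily for 5 days in total". Protocol 5.2.1 adds: "Oseltamivir or placebo should be dosed 12 hours apart from Day 1 through Day 5". The synopsis shows that adults in the S-033188 and placebo arms take dummy capsules on the same schedule. Only the 12 to 19 stratum receives one dose on Day 1 and nothing more.

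SAP 10.1 still uses the action-taken field. Its item 1) defines AEs leading to withdrawal of study drug as those recorded as drug withdrawn "in terms of the action taken for study drug". It summarises them per arm in the same way as AEs overall. Item 2) gives SOC/PT tables for all AEs, AEs at 2% or more, serious AEs, treatment-related AEs and serious treatment-related AEs. Item 3) crosses SOC/PT with onset, severity and outcome.

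**The concern.** A reason that is true of the test drug has been applied to the whole trial. The trial is double-dummy: an adult on S-033188 has a capsule course to stop, and an adult on oseltamivir has an active one. Stopping is also foreseen in the protocol. Section 7.8 covers withdrawal from study drug for AEs, 7.8.1 covers stopping blinded drug when open-label oseltamivir is given, and Appendix 5 covers stopping for abnormal liver tests.

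Comparing safety and tolerability with oseltamivir is a stated objective (Protocol 2.4, SAP 3.4). The Introduction argues that the five-day oral course may harm compliance and that the neuraminidase inhibitors are associated with nausea and vomiting. A table of which events led patients to stop active capsules, set against dummy capsules, speaks directly to that argument. It is the one part of the Protocol 9.11.1 summary that the SAP removes.

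**Working it through.** **Step 1. The planned total.** Inputs from Protocol 9.2 and SAP 4.3: infected-population targets of 875 (ages 20 to 64) and 93 (ages 12 to 19), and an RT-PCR positive rate of 65%.

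- Adults: 875 / 0.65 = 1346.2, stated as 1350.
- Adolescents: 93 / 0.65 = 143.1, stated as 144.
- Stated total: 1350 + 144 = 1494.

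The stated figures follow from the inputs with slight upward rounding. SAP 2 repeats them: "Approximately 1350 patients aged 20 to 64 years and 144 patients aged 12 to 19 years will be enrolled".

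**Step 2. Whom the stated reason fits.**

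- Single dose only: 144 / 1494 = 9.6%.
- Five-day capsule course: 1350 / 1494 = 90.4%.
- The same share in the infected population: 875 / 968 = 90.4%.

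**Step 3. What those adults take.** At 2:2:1, 1350 splits into 540 S-033188, 540 oseltamivir and 270 placebo.

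- Active oseltamivir capsules, no active S-033188: 540 / 1494 = 36.1%.
- Dummy capsules: (540 + 270) / 1494 = 54.2%.

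**Step 4. Sensitivity to the age mix.** Protocol 1.4 and 5.4 put adolescents at about 15% of everyone enrolled. The planned counts give 9.6%. The 15% matches 93 / 618 = 15.0%, the share among S-033188 and placebo patients only. If 15% did apply to the whole trial, the capsule share would be 100% - 15% = 85%.

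**Step 5. What survives in the SAP.**

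| Information on stopping for AEs | In the SAP? |
|---|---|
| Patients and proportion per arm, 95% CI, Fisher's test, event count | Yes, 10.1 1) |
| Individual cases | Yes, by-subject listings, 6.1 |
| Withdrawal AEs by SOC/PT | Not among the classes in 10.1 2) |
| Action taken by SOC/PT | Removed by 14; absent from 10.1 3) |

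**Step 6. Why the age stratum matters.** At 2:1, the 144 adolescents split into 96 S-033188 and 48 placebo, so the arms total 636 and 318. SAP 10.1 1) states no age restriction, and the safety age subgroup in 10.5 splits at 18, not 20. Assume that only adults can have study drug withdrawn. Then a given adult withdrawal rate appears at 540 / 636 = 0.85 of its value in the S-033188 arm and at 270 / 318 = 0.85 in the placebo arm, but in full in the oseltamivir arm. A table for ages 20 to 64 avoids this.

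**The case against.** The case against giving this much weight is substantial, and most of it stands.

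- The per-arm comparison of stopping for AEs is intact in SAP 10.1 1). A reader might infer that only a bare total remains, or that stopping is not reported at all. The SAP does not support either reading.
- Nausea and vomiting will be visible by arm, because all AEs and treatment-related AEs are tabulated by SOC/PT. SAP 8.1 summarises exposure duration for the S-033188 and oseltamivir groups, and SAP 7.1 tabulates reasons for leaving the study. None of these identifies the events that led to stopping the drug.
- SAP 1 places the table mock-ups in a separate document that is not available here. The point can be made only about what the SAP specifies, not about what will finally be produced.
- S-033188 is given once in both strata, so for the 540 adults in that arm the summary would show stopping of dummy capsules only. It would be too strong to say that the reason fails in the same way for all 1350. It fails most plainly for the 540 on oseltamivir. For the adults on dummy capsules it overlooks the rest of their course, which is the blinded comparison for oseltamivir.
- Protocol 9.11.1 does not ask for withdrawal AEs by SOC/PT, and it does not restrict any table to adults. Those would be additions. Drug withdrawn is also the only action category that the SAP names, so a category for interruption should not be assumed.
- The change is declared, as Protocol 9.1 requires, and SAP 1 says that decisions were made before unblinding. A reader might infer concealment or bias, but nothing in the documents suggests it.
- The table may be sparse. Protocol 1.3.1.2 says that most patients with the common oseltamivir reactions did not stop because of them.

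None of this makes the stated reason correct for adults or supplies the missing breakdown.

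**Conclusion.** The point holds as a limited gap in safety reporting. The reason in SAP 14 fits the 144 adolescents (9.6% of planned enrolment). It does not fit the 20 to 64 stratum, which is 90.4% on the planned counts, or about 85% on the 15% adolescent figure. As a result, no SOC/PT table specified in the SAP shows which events led to stopping study drug, although the trial sets out to compare tolerability with oseltamivir.

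The 90.4% measures who has a capsule course to stop, not who will stop. The documents give no expected number of stoppers, so the amount of information lost cannot be quantified. The conclusion rests on planned enrolment, on the allocation ratios and on the SAP text without its table shells. No efficacy test is affected. The change should still be made, because it restores a table that the protocol planned, from a field that the SAP already uses.

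**What to change.** 1. Correct the rationale in SAP 14 so that it applies only to the single-dose 12 to 19 stratum.
2. Reinstate the summary of action taken with study drug by SOC/PT and arm, as Protocol 9.11.1 plans, at least for ages 20 to 64. Mark it not applicable for ages 12 to 19. The age restriction is a choice made here for a like-for-like comparison; the protocol does not require it.
3. As a small addition beyond the protocol, add AEs leading to withdrawal of study drug to the classes tabulated by SOC/PT in SAP 10.1 2).

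The cost is one or two tables, possibly sparse, from data already collected. Restoring the summary returns to the protocol's own plan, so it needs a SAP revision but no protocol amendment.
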